Nicotine Replacement Therapy (NRT) helps combat nicotine withdrawal symptoms by providing users with nicotine in long-acting (patch) or short-acting (mask gum, lozenges, inhaler, nasal spray) form. Use of NRT in any form increases smoking abstinence by 60% compared to placebo (RR 1.60, 95% CI 1.53–1.68). To increase effectiveness, the nicotine patch can be combined with short-acting NRT, which is more effective than using a form of NRT (RR 1.34, 95% CI 1.18–1.51) (10). Bupropion increases norepinephrine and dopamine levels and is approved as an antidepressant for smoking cessation. Increases smoking cessation rates compared to placebo (OR 1.75, 95% CI 1.52 to 2.01) (8.9). Varenicline is a partial nicotinic receptor agonist that doubles smoking abstinence rates compared to placebo (RR 2.24, 95% CI 2.06–2.43). (10) These results have been obtained in smokers treated on an outpatient basis. The study of the effectiveness of these different treatments in hospitalized subjects has been little and marginally analyzed.(6) Among the studies carried out, it shows that hospitalized subjects who received treatment for smoking cessation and support had abstinence rates greater than 6 months. The analysis carried out in this study does not differentiate by type of pharmacological treatment. The predominant pharmacological treatment was NRT. (11) Smoking cessation in hospitalized patients has been associated with lower rates of postsurgical complications, better tissue healing and proliferation, and reversibility of the attenuation of inflammation mechanisms. (12,13)

Hospitalization is a vital scenario to address tobacco consumption for various reasons and benefits; among the most important are the prohibition of smoking on the hospital premises and the special availability for quitting that the smoker has during admission to a hospital admission promotes subsequent tobacco cessation because a severe illness, primarily if related to tobacco, can increase smokers' motivation to quit.

MAIN OBJECTIVE

Our objective will be to analyze the effectiveness of the combination of bupropion and nicotine versus nicotine replacement therapy to quit smoking in hospitalized subjects 12 months after discharge.

SPECIFIC OBJECTIVES

1. Analyze the effectiveness of the combination of pharmacological therapies to quit smoking in hospitalized subjects 3, 6 and 12 months after discharge.
2. Evaluate the symptoms and signs of withdrawal in the different groups throughout their follow-up.
3. Record the adverse effects of the different pharmacological therapies reported in the different groups throughout their follow-up.
4. Evaluate the lung function of the different groups at 3 months after discharge, 6 months and 12 months after discharge.

METHODS

a) Location of the study.

National Institute of Respiratory Diseases, Ismael Cosío Villegas México.

Smoking and COPD Research Department.

b) Description of the population:

Inclusion criteria:

1. Over 18 years of age.
2. Active smokers (smoking more than 100 cigarettes in their entire life and having consumed cigarettes in the last 30 days)
3. Hospitalized subjects with acute or chronic lung disease.
4. Signing of informed consent.

Exclusion criteria:

1. Subjects with pharmacological treatment to stop smoking during recruitment or in the last month.
2. Contraindications to the use of pharmacological therapy. (Annex is attached the contraindications for the use of medications)
3. Subjects who cannot maintain follow-up.

Elimination criteria:

1. In an analysis by intention to treat, there will be no elimination of subjects after randomization.

Sample size:

The sample size calculation is carried out by difference between proportions, with a confidence level of 95%, power of 80%, unilateral, with an observed proportion of 65% and an expected proportion of 80% for the combination of pharmacological therapy; 50 subjects are required for each group; If a loss of participants is estimated at 25%, 67 subjects are required for each group. The sample size was carried out in the WinEpi 2006 program.

c) Outcome variables and description of other study variables.

Outcome variable:

-Abstinence: abstinence from tobacco is defined as its suspension 12 months after hospital discharge, corroborated by detection of exhaled carbon monoxide less than 7 ppb and/or detection of cotinine in urine (positive).

-Active smoker: defined as an active smoker who has consumed more than 100 cigarettes in his or her entire life and who has consumed cigarettes in the last 30 days.

-CBT (cognitive behavioral therapy) is a model for treating problematic behaviors that focuses primarily on identifying and changing maladaptive patterns of behavior and thoughts, including problem-solving and coping skills rooted in relapse prevention theory, along with the cognitive restoration of maladaptive thoughts to regulate emotions and is combined with the recommendations of the Clinical Practice Guideline (CPG) for tobacco.

(14)

-Acute or chronic lung disease: Acute or chronic lung disease will be considered by medical diagnosis.

-Exhaled carbon monoxide: a value greater than or equal to 7 ppb is defined as positive (subject with active smoking).

-Cotinine in urine: defined as positive (subject with active smoking) positive test (qualitative test)

-Nicotine dependence (Fagerström Questionnaire): mild, moderate and severe.

-Withdrawal symptoms questionnaire.

-Nicotine Craving Questionnaire (Urge to smoke, understood as a physiological and motivational state that drives the desire to smoke tobacco).

-Adverse reactions questionnaire.

-Respiratory symptoms questionnaires (PLATINO).

-Pulmonary function tests (pre- and post-bronchodilator spirometry, carbon monoxide diffusion, and 6-minute walk)

-Beck Anxiety and Depression Questionnaires.

Procedures for collecting information using instruments and data quality control methods.

Data Capture.

a)

b) 1-Subject identification (inclusion/exclusion criteria)

c) 2-Signature of informed consent

d) 3-Randomization of the drug (2 groups: a-nicotine patches, b-combination: nicotine patches + bupropion)

e) 4-Start hospitalization treatment

f) - Processes: Medications are given in a personalized way during hospitalization; brief advice is given, and questionnaires and measurements of exhaled CO and cotinine in urine are performed (treatment start day is day 0). The pharmacological treatment given to the subject will be for at least 12 weeks.

g) 5-Monitoring during hospitalization to provide medications

- h) 6-Upon discharge, an appointment is made at the Smoking Clinic within the first 14 days of discharge, and anti-smoking treatment for home use and brief advice will be provided.
- i) 7-First appointment at the Smoking Clinic
- j) - Processes: brief advice; intake of exhaled CO and cotinine in urine). It is scheduled to begin cognitive behavioral therapy (CBT) in a group, which lasts ten sessions, two times a week, with mixed modality (online or in-person).
- k) 8-Start CBT in the next two weeks after discharge.
- l) 9- Second appointment at the Smoking Clinic at the end of therapy (3 months after discharge)
- m) - Processes: brief advice; questionnaires and measurement of exhaled CO and cotinine in urine are performed; pre- and post-bronchodilator spirometry, carbon monoxide diffusion, 6-minute walk.
- n) 10-Third appointment at the Smoking Clinic 6 months after discharge:
- o) - Processes: brief advice; questionnaires and measurement of exhaled CO and cotinine in urine are performed; pre- and post-bronchodilator spirometry, carbon monoxide diffusion, 6-minute walk)
- p) 11-Fourth appointment at the Smoking Clinic 12 months after discharge
- q) - Processes: brief advice; questionnaires and measurement of exhaled CO and cotinine in urine are performed; pre- and post-bronchodilator spirometry, carbon monoxide diffusion, 6-minute walk)
- r) The information collection will be carried out through the INER RedCAP platform, which has security mechanisms for the data obtained and methods for adequate control. The protocol researchers will carry out data capture.

Results analysis plan.

1- A retrospective analysis was carried out on hospitalized patients with a history of active smoking, with the following characteristics: 40% of the patients evaluated had low dependence on nicotine, and 60% had moderate and severe dependence. Of the patients evaluated, 72% were male, and 28% were female. Proportional allocation is carried out for stratified sampling, Stratified randomization for sex (man and woman), and for low and moderate/severe dependence

2- Statistical analysis methods according to the type of variables: the variables will be analyzed according to their type of distribution and whether they are quantitative or qualitative, by student's t or chi2 as appropriate. A descriptive analysis will be carried out on each of the variables. Subsequently, a comparative analysis will be carried out between the 2 groups included, using ANOVA or Kruskal Wallis, depending on their distribution. The analysis of the main objective will be carried out by intention to treat according to the treatment granted and randomization. Randomization was stratified by level of nicotine dependence and sex. There will be no blinding. The primary outcome will be abstinence at 12 months, and its association with the randomized treatment group will be seen. As a complementary analysis, a per-protocol analysis will be performed according to the treatment received. Finally, through multivariate analysis by logistic regression, abstinence or non-abstinence at one year was analyzed depending on the treatment received, adjusted for the different covariates such as sex, age, smoking rate, and level of dependence.

3-The statistical analysis will be carried out using the STATA V13 statistical package.

ETHICAL CONSIDERATIONS

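### Adverse effects are to be recorded throughout follow-up, but no step captures serious events or drug stopping in patients who do not return

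*Combined protocol and SAP*

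**What the plan says.** The combined protocol and SAP treats safety in four places.

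- **Specific objectives, item 3.** The aim is to "Record the adverse effects of the different pharmacological therapies reported in the different groups throughout their follow-up".
- **Methods c), list of variables.** One line names the instrument: "Adverse reactions questionnaire". Its content, recall period and grading are not described.
- **Data Capture, steps 4 to 11.** In hospital, "questionnaires and measurements of exhaled CO and cotinine in urine are performed (treatment start day is day 0"). Step 5 is "5-Monitoring during hospitalization to provide medications", so its stated purpose is supply. The first clinic appointment, within 14 days of discharge (step 7), lists "Processes: brief advice; intake of exhaled CO and cotinine in urine" and no questionnaire. At the 3-, 6- and 12-month appointments (steps 9 to 11), "questionnaires and measurement of exhaled CO and cotinine in urine are performed". On duration: "The pharmacological treatment given to the subject will be for at least 12 weeks".
- **Methods b), Sample size.** "If a loss of participants is estimated at 25%, 67 subjects are required for each group".

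The Results analysis plan states that there is no blinding. It specifies intention to treat for the main objective and a complementary per-protocol analysis by treatment received. It contains no analysis specific to adverse effects.

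**The concern.** An objective that covers all of follow-up is served by an instrument that works only when the patient attends. The participants are recruited while in hospital with lung disease, so death and readmission are foreseeable, and both can prevent attendance. A reaction that leads someone to stop the drug may also lead that person to stop coming.

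If such patients contribute no data, the reported event rates describe attendees and not everyone randomised. Keeping all patients in the denominator does not supply the missing safety information. The per-protocol analysis is affected too: it needs to know what treatment was taken, yet no step records when or why study drug stopped.

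**Working it through.** **1. The plan's own figure.** Inputs from the Sample size section: 50 per group before loss, 25% loss. 50 / (1 − 0.25) = 66.7, rounded up to 67. This reproduces the plan. The implied loss is 67 − 50 = 17 per arm, or 34 of 134 in total.

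**2. What each contact lists for safety.**

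| Contact | Questionnaires listed? | Vital status, readmission, or date and reason for stopping? |
|---|---|---|
| Treatment start in hospital (day 0) | Yes | No |
| Monitoring in hospital | No | No |
| Clinic, within 14 days of discharge | No | No |
| CBT, ten sessions | No | No |
| Clinic, month 3 | Yes | No |
| Clinic, months 6 and 12 | Yes | No |
| Missed visit | No procedure given | No procedure given |

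The steps say only that questionnaires are done. That these include the adverse reactions questionnaire is the natural reading, but it is not stated. After day 0 the next listed questionnaire is three months after discharge, so the minimum 12 weeks of treatment depends on recall by those who return.

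**3. What the 25% bounds.** It is a planning allowance for a trial with a 12-month endpoint. Patients lost between month 3 and month 12 will already have completed the month-3 questionnaire. If lost patients stay lost and realised loss does not exceed the allowance, those lacking month-3 data number at most 17 of 67 per arm. The document does not say how many would be lost by then.

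**4. How far absolute rates could be under-counted.** Let f be the share of patients with no record and r the event risk in that group divided by the risk in attendees. The share of affected patients not recorded is f·r / [(1 − f) + f·r]. The documents give no event risks, so r is an assumption. At the upper bound f = 0.25:

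- r = 1: 0.25 / 1.00 = 25%
- r = 2: 0.50 / 1.25 = 40%
- r = 3: 0.75 / 1.50 = 50%
- r = 4: 1.00 / 1.75 = 57%

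A smaller f gives smaller shares. These figures bound the problem; they do not forecast it.

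**5. Whether the direction between arms can be stated.** Take assumed true risks of 30% and 15%, used only to test direction, with 25% loss in each arm and affected patients k times as likely to be lost. The risk among attendees is p(1 − k·l)/0.75, where l = 0.25/[(1 − p) + k·p].

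| k, higher-risk arm | k, lower-risk arm | Seen in attendees | Difference (points) | Ratio |
|---|---|---|---|---|
| 1 | 1 | 30% vs 15% | 15 | 2.00 |
| 2 | 2 | 24.6% vs 11.3% | 13.3 | 2.18 |
| 3 | 3 | 21.3% vs 8.5% | 12.8 | 2.51 |
| 3 | 1 | 21.25% vs 15% | 6.25 | 21.25/15 = 1.42 |
| 1 | 3 | 30% vs 8.5% | 21.5 | 30/8.46 = 3.55 |

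With the same k in both arms, the difference falls while the ratio rises. When k differs between arms, the bias can go either way.

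**The case against.** The strongest case on the other side has four parts.

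- **The objective is modest.** It is to record effects that are reported, and intention to treat is specified only for the main objective. The plan does not promise a comparison of deaths and readmissions on all randomised patients, and all-cause events are broader than drug effects. This stands as a limit. However, patients who do not return have no written way to report drug effects either, and the objective covers the whole of follow-up.
- **There are other contacts.** Ward monitoring, the 14-day visit and the CBT sessions bring staff and patients together, and people who cannot maintain follow-up are excluded. Staff may well learn of events this way. None of these contacts is written as a capture route, so what is learned would be unsystematic and, without blinding, could differ by arm.
- **The 25% is not on-treatment loss.** This stands. A reader might infer that 17 patients per arm would have no drug-reaction data. The document does not support that, because month 3 falls at about the end of the minimum treatment period and later losses will already have completed that questionnaire.
- **Silence is not proof of loss.** This also stands. A reader might infer that deaths after discharge would be missed entirely. A questionnaire completed by the patient cannot record that patient's death, but staff could hear of it by other means; the plan does not say.

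A further tempting inference is that the combination arm would look safer than it is. The document gives no loss by arm and no event risks. Step 5 of the working shows that equal loss raises the ratio against the higher-risk arm, and that unequal loss can push the comparison either way.

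**Conclusion.** The concern holds as a gap in ascertainment. Followed as written, the plan gives no systematic way to capture serious events or drug stopping in patients who do not return. Absolute event rates are likely to be under-counted, and the open-label safety comparison rests on attendees. The direction of any bias between arms is unknown.

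The size cannot be estimated from the document. The plan's allowance puts an upper bound of 17 of 67 per arm on those without month-3 data, assuming that lost patients stay lost and that loss does not exceed 25%. Under-counting is likely only if patients who leave have events unrecorded at their last attended visit, which is plausible in this population but not demonstrated. The finding covers the supplied text only; the contraindications annex and some front matter were not available. It affects a secondary objective and the per-protocol analysis, not the primary endpoint, so the change is advisable and cheap.

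**What to change.** - **Steps 9 to 11:** for every randomised patient, including those who miss the visit, record vital status, any readmission, and the date and reason for stopping study drug. Use the institute's own hospital record and one telephone contact by the existing team.
- **Step 7:** add the adverse reactions questionnaire to the visit within 14 days of discharge.
- **Results analysis plan:** report deaths, readmissions and stopping for adverse effects by randomised arm on all randomised patients, and give the number in each arm with no safety information.

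The cost is three or four extra REDCap fields, one more questionnaire at an existing visit, a chart check, and one call per missed visit. The downside is a little more follow-up work, and readmissions to other hospitals will be known only from the call. The change concerns data collection and reporting; it alters no treatment.

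### Lung function (objective 4) is compared between arms with no pre-treatment test and no adjustment for diagnosis, so the comparison is unbiased but imprecise; a covariate-adjusted repeated-measures model is a cheap improvement

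*Combined protocol and SAP*

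**What the plan says.** All references are to the combined protocol and SAP.

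- **Objective** (Specific Objectives, item 4): "Evaluate the lung function of the different groups at 3 months after discharge, 6 months and 12 months after discharge". No change from a starting value is mentioned.
- **Measures** (Outcome variables and description of other study variables): "Pulmonary function tests (pre- and post-bronchodilator spirometry, carbon monoxide diffusion, and 6-minute walk". No time point, leading parameter, SD or target difference is given there.
- **Day 0** (Data Capture, step 4): "brief advice is given, and questionnaires and measurements of exhaled CO and cotinine in urine are performed (treatment start day is day 0". No lung function test is listed.
- **First clinic visit**, within 14 days of discharge (step 7): "brief advice; intake of exhaled CO and cotinine in urine". Again no lung function test.
- **First lung function test** (step 9): "Second appointment at the Smoking Clinic at the end of therapy (3 months after discharge". The tests are repeated at 6 and 12 months (steps 10 and 11).
- **Population** (Inclusion criteria, item 3): "Hospitalized subjects with acute or chronic lung disease". The variable list says this is established by medical diagnosis.
- **Stratification** (Results analysis plan, item 2): "Randomization was stratified by level of nicotine dependence and sex". Diagnosis is not a factor.
- **Analysis** (same item): t test or chi-square by type of variable, then "a comparative analysis will be carried out between the 2 groups included, using ANOVA or Kruskal Wallis, depending on their distribution". The only adjusted model is the logistic regression for one-year abstinence, and its named covariates include neither diagnosis nor lung function.

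**The concern.** The first lung function value comes 3 months after discharge. Treatment starts in hospital and lasts at least 12 weeks, so no value precedes treatment. Patients with acute and with chronic lung disease can be expected to differ widely in lung function at the follow-up visits. An unadjusted comparison leaves all of that spread in the error term.

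Two things are at stake. The arm estimates will have wide confidence intervals. And if one arm happens to hold more patients with poor lung function, the planned analysis does nothing to allow for it, so a chance difference could be read as a drug effect. Because no earlier test is scheduled, an imbalance in starting lung function could not even be seen.

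**Working it through.** **Inputs from the documents.** 50 evaluable patients per arm; 67 after allowing for 25% loss; abstinence of 65% and 80%. The loss step reproduces: 50 / (1 − 0.25) = 66.7, so 67. Whether 50 is enough for the primary outcome is a separate question, and 50 and 67 are taken as given here. The documents give no sample size for lung function, so there is no plan figure to reproduce.

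**Assumptions.** Two-sided 5% and 80% power, because sidedness is stated only for the primary sample size. Results are in SD units because no SD is given. The correlation r between a prior value and the follow-up value is not in the documents and is varied from 0.3 to 0.8.

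**Step 1: precision as planned.** SE of the arm difference = SD × √(2/n).
- n = 50: √(2/50) = 0.200 SD; 95% CI half-width 1.96 × 0.200 = 0.39 SD; detectable difference (1.960 + 0.842) × 0.200 = 0.560 SD.
- n = 67: √(2/67) = 0.173 SD; detectable difference 0.484 SD.
- At one-sided 5%, n = 50 gives (1.645 + 0.842) × 0.200 = 0.497 SD.

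**Step 2: gain from a covariate.** The residual SD becomes SD × √(1 − r²), so the detectable difference is multiplied by the same factor.

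| r | r² | √(1 − r²) | Detectable, n = 50 | Detectable, n = 67 |
|---|---|---|---|---|
| 0 | 0 | 1.000 | 0.560 SD | 0.484 SD |
| 0.3 | 0.09 | 0.954 | 0.535 SD | 0.462 SD |
| 0.5 | 0.25 | 0.866 | 0.485 SD | 0.419 SD |
| 0.7 | 0.49 | 0.714 | 0.400 SD | 0.346 SD |
| 0.8 | 0.64 | 0.600 | 0.336 SD | 0.290 SD |

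The same table can be read for diagnosis class and the other covariates together, with r² as the share of variance that they explain. For a prior spirometry value the gains are upper bounds: they assume a value in every patient, whereas some will be missing or taken during acute illness.

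**Step 3: chance imbalance.** The probability that the arms differ by more than 0.2 SD in true starting lung function is 2 × [1 − Φ(0.2/0.200)] = 32% with 50 per arm, and 2 × [1 − Φ(0.2/0.173)] = 25% with 67.

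**Step 4: size of effect to expect.** Assume that treatment changes lung function only through extra quitters. The planned abstinence difference is 0.80 − 0.65 = 0.15, so the arm difference is 0.15 × the effect of quitting. The effect of quitting is not in the documents; a range is shown for n = 50. Power is Φ(d/SE − 1.96) + Φ(−d/SE − 1.96), where d is the arm difference.

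| Assumed effect of quitting | Arm difference d | Power unadjusted (SE 0.200) | Power at r = 0.8 (SE 0.120) |
|---|---|---|---|
| 0.25 SD | 0.0375 SD | 5.4% | 6.1% |
| 0.5 SD | 0.075 SD | 6.6% | 9.6% |
| 1 SD | 0.15 SD | 11.7% | 24.0% |

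Even the last row is well below the 0.336 SD detectable at r = 0.8.

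**The case against.** The case for leaving the plan alone has several parts.

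- **Randomisation protects the comparison.** This stands. A reader might infer that recovery from acute illness biases the arm comparison. The documents do not support that: recovery should be alike in both randomised arms in expectation, so it adds noise and not bias.
- **Objective 4 promises no change score.** This stands. A reader might infer that the objective fails because change since treatment start cannot be estimated. The text asks for lung function at three visits, and levels by arm can be reported as planned. A late level may also be easier to interpret than a test done during an acute admission.
- **A prior value would not rescue the objective.** This stands too, as step 4 shows. The binding limit is dilution through a 15-point abstinence difference. A reader who blames the missing baseline alone would expect too much from adding one.
- **Diagnosis is already a study variable, and every variable is to be described.** This stands in part. An acute/chronic imbalance should be visible in the descriptive tables, but no analysis adjusts for it.

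What remains is narrower: the only analysis named for these measures is unadjusted, although a relevant covariate is already on the variable list.

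**Conclusion.** The point holds as a minor one. The planned comparison of lung function is unbiased in expectation but imprecise: 0.56 SD is detectable with 50 per arm and 0.48 SD with 67. It does not allow for chance imbalance in diagnosis. Adjustment improves this by an amount that depends on how much variance the covariates explain, which the documents do not say: little at r = 0.3 to 0.5, more at 0.7 to 0.8.

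Whether differences between patients overwhelm the comparison is a matter of degree that cannot be settled without an SD. Nor do the documents support the claim that the fix would make an effect on lung function detectable. If the effect acts only through quitting, even an assumed 1 SD benefit of quitting has about 12% power unadjusted and 24% at r = 0.8. The primary outcome, abstinence at 12 months, is not affected.

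**What to change.** In the Results analysis plan, replace the unadjusted comparison for objective 4 with the following.

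1. Analyse spirometry and diffusion (as % predicted) and walk distance by randomised arm. Use one repeated-measures model per measure over 3, 6 and 12 months, with arm, visit and arm-by-visit terms, adjusted for acute/chronic diagnosis class, age, and the stratification factors sex and dependence level. Record diagnosis class as its own coded field in REDCap, fixed before randomisation, with a stated rule for patients who have both.
2. Optionally, where the hospital record already holds a spirometry value from before randomisation, add it as a covariate with a missing indicator. This is acceptable because whether the value exists is settled before allocation. The documents do not say how often such values exist, and none is offered for diffusion or walk distance.
3. State that the result is the level after treatment and not the change from treatment start. Present arm differences with 95% confidence intervals, and do not read the absence of a significant difference as absence of an effect.

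Cost: one coded field, analysis wording and, if item 2 is taken up, abstraction of one value per patient. No extra test, visit or patient is needed.

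### The rise from 50 to 67 per group for 25% loss is tied to no stated rule for a missing 12-month result, and the claimed 80% power is not reached under any reading examined

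*Combined protocol and SAP*

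**What the plan says.** All references are to the combined protocol and SAP.

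- **Methods, Elimination criteria:** "In an analysis by intention to treat, there will be no elimination of subjects after randomization".
- **Results analysis plan, item 2:** "The analysis of the main objective will be carried out by intention to treat according to the treatment granted and randomization". The primary outcome is abstinence at 12 months, the regression treats it as two categories, and there is no blinding.
- **Methods, Sample size:** 65% against 80%, "with a confidence level of 95%, power of 80%, unilateral", giving 50 per group. Then: "If a loss of participants is estimated at 25%, 67 subjects are required for each group".
- **Methods, Exclusion criteria:** "Subjects who cannot maintain follow-up" are not enrolled.
- **Methods, Outcome variable:** abstinence must be "corroborated by detection of exhaled carbon monoxide less than 7 ppb and/or detection of cotinine in urine (positive". The later entry for exhaled carbon monoxide says "a value greater than or equal to 7 ppb is defined as positive (subject with active smoking", and the next entry treats a positive cotinine test in the same way, as active smoking.

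The plan gives no rule for a randomised patient with no 12-month carbon monoxide or cotinine result. It does not say whether 65% and 80% are rates among all randomised or among those followed. The analysis section does not say whether the primary test is one- or two-sided.

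**The concern.** The sample-size step and the analysis set rest on different ideas of what happens to a lost patient. Dividing by 0.75 supposes that the lost contribute nothing and that the remaining 50 or so per group keep rates of 65% and 80%. Intention to treat with nobody eliminated supposes that all 67 count, which needs an outcome for each of them.

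The plan expects a quarter of patients to be affected, so the unstated rule matters for the primary result and not only for its power. Counting the lost as not abstinent shrinks the difference to be detected. Leaving them out biases the comparison when loss depends on outcome, and under no true effect that bias does not cancel if the dependence differs between arms. In an unblinded trial, equal amounts of loss and equal reasons for it cannot be taken for granted. A rule that is not fixed in advance can be chosen after the data are seen.

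**Working it through.** **Inputs.** From the sample-size paragraph: rates 65% and 80%, 95% confidence, one-sided, 80% power, 50 per group, 25% loss, 67 per group. Equal allocation is inferred from the equal group sizes. Equal loss in the two arms is an assumption, except where stated.

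**The plan's own figures.** 50/(1 − 0.25) = 66.7, so 67 follows from 50. The 50 does not follow from the stated inputs. With p̄ = 0.725 and a pooled two-proportion test,

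n = [1.645·√(2·0.725·0.275) + 0.842·√(0.65·0.35 + 0.80·0.20)]² / 0.15² = 108.5, so 109 evaluable per group.

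Variants of the two-group formula give 107 (unpooled), 108 (arcsine) and 122 (continuity-corrected). Two-sided, the pooled formula gives 138.

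**Power under each reading.** Power = Φ{[p₂ − p₁ − z·√(2p̄(1 − p̄)/n)] / √([p₁(1 − p₁) + p₂(1 − p₂)]/n)}, with z = 1.645 one-sided or 1.960 two-sided.

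| Reading | n per group | Rates | One-sided | Two-sided |
|---|---|---|---|---|
| Lost left out | 50 | 65% vs 80% | 51.4% | 38.8% |
| Rates apply to all randomised | 67 | 65% vs 80% | 61.9% | 49.4% |
| Rates apply to those followed; lost counted as not abstinent | 67 | 48.75% vs 60% | 36.7% | 25.6% |
| Rates apply to those followed; lost counted as abstinent | 67 | 73.75% vs 85% | 48.6% | 36.2% |

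Exact enumeration of the first three one-sided figures gives 52.2%, 62.9% and 36.7%.

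The third row comes from 0.75 × 0.65 = 0.4875 and 0.75 × 0.80 = 0.60, a difference of 11.25 points instead of 15. At other equal losses the one-sided power under that rule is about 50% (10% loss) and 30% (35% loss).

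**Separating the two causes.** From 80% to 51% is the base-size error. From 51% to 37% is loss handling. The second effect does not depend on the first: starting from a correct 109, dividing by 0.75 gives 146 per group, and counting the lost as not abstinent then gives 61.3% one-sided power, not 80%.

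**A constraint between rule and rates.** If 25% of an arm are lost and counted as not abstinent, abstinence among all randomised cannot exceed 75%. An 80% rate among all randomised, 25% loss and this rule cannot all hold.

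**How the choice moves the estimate.**
- *Leaving out the lost, loss related to outcome.* With 25% lost per arm, all of them smoking, complete-case analysis shows 15 points where the difference among all randomised is 11.25. With no true effect (assumed 50% abstinent in each arm, 25% lost in each), suppose all the lost smoke in one arm and half are abstinent in the other. The analysis then shows 0.50/0.75 = 66.7% against (0.50 − 0.125)/0.75 = 50%.
- *Leaving out the lost, loss unrelated to outcome.* With 65% abstinent in both arms and 30% vs 20% random loss (47 vs 54 analysed), exact one-sided rejection is 4.8%. Unequal loss alone does no harm here.
- *Counting the lost as not abstinent, unequal loss.* With 30% loss on nicotine replacement, 20% on the combination, and 65% abstinent among those followed in both arms, the rates become 45.5% vs 52%, and one-sided rejection is about 19%. That is a false difference only if the lost are in truth abstinent at the same rate as those followed. If they are smoking, the difference is real.

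**The case against.** The best defence is that the rule can be read from the text. Abstinence requires corroboration, the outcome has two categories and nobody is eliminated, so an uncorroborated patient falls among the non-abstinent. This has weight: the text leans that way, and a reader who infers that the definitions leave the matter wholly open goes too far. But the rule is an inference and is not written. An untested patient does not meet the test-based definition of active smoking either. If the rule was intended, the division by 0.75 does not fit it.

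The opposite inference, that the sponsor meant a complete-case analysis because 67 × 0.75 is about 50, is no better supported, since the plan nowhere names such an analysis.

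A second objection is that most of the shortfall has nothing to do with missing results. That stands. A reader might attribute the whole drop from 80% to 37% to the missing rule, but its share is 51% to 37%, and only if the rates describe those followed. If they describe all randomised, power at 67 is about 62%.

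A third is that excluding patients who cannot maintain follow-up limits loss. It may, but the plan still expects 25% after that exclusion.

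**Conclusion.** The point holds as an omission together with a wrong power figure. The inflation to 67 fits an analysis that drops the lost, the stated analysis drops nobody, and no rule connects the two. The 80% is not met under any reading examined: the one-sided range is about 37% to 62%, and the two-sided range about 26% to 49%. The 37% assumes equal 25% loss per arm and rates that describe those followed. The 62% assumes rates that describe all randomised, and that reading is incompatible with 25% loss counted as not abstinent.

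The one-sided figures follow the sample-size paragraph. Because the analysis section names a chi-squared test without stating sidedness, neither column can be called the plan's power until that is settled. The documents do not show which missing-result rule was intended, nor that unequal loss by itself would bias a complete-case analysis.

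**What to change.** Keep 67 per group and amend the text in this order.

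1. Reconcile the cotinine wording. The outcome definition accepts a positive result as corroborating abstinence, while the later entry defines positive as active smoking. Until this is settled, a verified result has no clear meaning.
2. State the rule, for example: the primary intention-to-treat analysis includes all randomised patients, and those without a verified 12-month result are counted as not abstinent. Another explicit rule would also close the gap if the power is restated to match.
3. Add sensitivity analyses: multiple imputation using arm, sex, dependence and 3- and 6-month status, and complete case. Report loss by arm. Note beside the rule that unequal loss can create a false difference, as shown in the working.
4. Say whether 65% and 80% apply to all randomised or to those followed, and whether the primary test is one- or two-sided.
5. Replace the 80% claim with the matching figure at 67 per group. Under the rule in step 2 this is about 37% (26% two-sided) if the rates apply to those followed, or about 62% (49%) if they apply to all randomised. In the latter case the 25% loss assumption must also be revised, because of the 75% ceiling.

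The cost is wording, a few extra analyses and a less favourable stated power. Counting the lost as not abstinent is itself an assumption, which is why the sensitivity analyses are needed. This point asks for no larger trial. For information only, 80% one-sided power at 48.75% vs 60% would need 242 per group.
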